## 8. DATA MANAGEMENT

Data Management is the responsibility of the Medical University of Graz, Department of Endocrinology and Diabetology and the study Monitor. The subject and the biological material obtained from the subject will be identified by subject number, trial site and trial identification number. Appropriate measures such as encryption or deletion will be enforced to protect the identity of human subjects in all presentations and publications as required by local/regional and national requirements.

This study will capture and process data using an electronic Case Report Form (Clincase) which is a fully validated high quality electronic data capture system, which has a full audit trail and controlled level of access. Data and reports will be extracted from the database throughout the study to monitor progress and training will be provided to all study staff on use of the database.

Protocol No: Version 2.17

#### Date: 17 October 2022

#### 9. TREATMENT

#### 9.1 Study medication

Empagliflozin is a sodium-glucose cotransporter 2 (SGLT2)-inhibitor. It works by increasing the amount of sugar that leaves the body in the urine. The study dose is 10mg once daily in the morning, taken with or without food. Each tablet contains 10mg Empagliflozin or Placebo. The pharmaceutical form is a round, pale yellow, biconvex, beveledged film-coated tablet debossed with "S10" on one side and the Boehringer Ingelheim logo on the other (tablet diameter: 9.1 mm). Empagliflozin has minor influence on the ability to drive and use machines. Patients should be advised to take precautions to avoid hypoglycemia while driving and using machines, in particular when Empagliflozin is used in combination with a sulfonylurea and/or insulin. Pharmacy (Anstaltsapotheke) at the University Hospital of Graz, Austria will pack the medication as 26 weeks supplies for study participants and label study medication according to current regulatory requirements.

#### 9.2 Method of administration

The tablets can be taken with or without food, swallowed whole with water. If a dose is missed, it should be taken as soon as the patient remembers. A double dose should not be taken on the same day.

#### 9.3 Special precautions for storage

The study drug must be kept locked in a locked secure area. For this study drug no particular storage conditions are required.

#### 9.4 Dispensing of Study Drug

The study team shall dispense the study drug only to subjects entered into the study, under the direction of the PI or sub-investigators authorized to receive or dispense it. The study drugs will not be dispensed or supplied to any person not authorized to receive it. Each time a study drug is dispensed; there must be documentation in the sponsor provided log (drug accountability log) as to the amount dispensed, to whom it is dispensed, and the date and signature or initials of the person dispensing the drug. Subjects should be advised to follow the study protocol and as appropriate to protocol return all used and unused containers to the site at study visit 4 (week 26). Any discrepancies between the amounts used by the subjects and the amount returned should be documented.

## 9.5 Return/Destruction of Study Drug

Assure that unused supplies of the study drug are returned to the sponsor in accordance with sponsor requirements. Obtain authorization from the sponsor if unused supplies of the study drug will be disposed of at the end of the study. Maintain records of the return or disposition of the unused study drug, including the unused study drug amount, lot numbers and quantity, method of return or disposition, and any documentation related to shipment or destruction. At the end of the study ensure that all documentation regarding receipt, storage, dispensing, return of used containers, and accountability is complete and accurate.

Protocol No: Version 2.17 Date: 17 October 2022

#### 10. REGULATORY, ETHICAL AND LEGAL ISSUES

10.1 Declaration of Helsinki

The investigator will ensure that this study is conducted in full conformity with the 1964 Declaration of Helsinki and all subsequent revisions.

10.2 Good Clinical Practice

The study will be conducted in accordance with the guidelines laid down by the International Conference on Harmonisation for Good Clinical Practice (ICH GCP E6 guidelines).

10.3 Independent Ethics Committee/ competent authority

## 10.3.1 Initial Approval

Prior to the enrolment of subjects, the Ethics Committee at the Medical University of Graz must provide written approval of the conduct of the study at named sites, the protocol and any amendments, the Patient Information Sheet and Consent Form, any other written information that will be provided to the subjects, any advertisements that will be used and details of any subject compensation.

#### 10.3.2 Approval of Amendments

Proposed amendments to the protocol and aforementioned documents must be submitted to the Ethics Committee for approval as instructed by the Sponsor. Amendments requiring approval may be implemented only after a copy of the approval letter has been obtained.

Amendments that are intended to eliminate an apparent immediate hazard to subjects may be implemented prior to receiving Sponsor or the Ethics Committee approval. However, in this case, approval must be obtained as soon as possible after implementation.

#### 10.3.3 Competent Authority

Clinical Trial Applications (EudraCT application and the documents required for the assessment) should be addressed to the Austrian Competent Authority, the Federal Office for Safety in Health Care (Bundesamt für Sicherheit im Gesundheitswesen, BASG) under the following address:

Austrian Federal Office for Safety in Health Care (BASG)
Austrian Agency for Health and Food Safety (AGES)
Institute Surveillance (INS), Department for Clinical Trials (CLTR)
[name]
[name]
Austria

10.4 Insurance

Participant insurance according to legal requirements will be contracted.

## 10.5 Informed Consent

The participation of a subject in this clinical trial is voluntary. The investigator or a member of the research team will approach the patient to obtain informed consent. The background of the proposed study, the procedure, the follow-

Protocol No: Version 2.17 Date: 17 October 2022

up schedule and all potential benefits and risks will be carefully explained to each subject. The person obtaining the informed consent shall:

- Avoid any coercion or undue influence of subjects to participate
- Not waive or appear to waive subject's legal rights
- Use language that is non-technical and understandable to the subject
- Clarify the subject that his/her data are confidential and are encoded with a subject ID number during the investigation
- Provide plenty of time for the subject to consider his/her participation
- Include dated signatures of the subject and of the clinical investigator
- Ask whether the subject has any questions about the study

After a subject has received and read the patient information sheet and agrees to participate in the study, the informed consent form approved by the Ethics Committee must be signed by the subject prior to any study specific tests being performed. It will also be signed by the person responsible for collecting the informed consent. The original will be kept in the subjects study research notes (source documents), a copy will be given to the subject and a copy kept in their hospital notes.

## 10.6 Subject Confidentiality

The investigator must ensure that the subject's privacy is maintained. On the CRF or other documents submitted to the Sponsors, subjects will be identified by a subject ID number only. Documents that are not submitted to the Sponsor (e.g., signed informed consent form) should be kept in a strictly confidential file by the investigator. The investigator shall permit direct access to subjects' records and source document for the purposes of monitoring, auditing, or inspection by the Sponsor, authorised representatives of the Sponsor, Regulatory Authorities and Ethic Committees.

## 10.7 End of Trial

The trial will end after the last subject has completed the follow-up telephone assessment (Study visit 5). All patients will be reviewed by a clinician at their last study visit in order to arrange return to appropriate routine clinical care pathways.

## 10.8 Study Documentation and Data Storage

The investigator must retain essential documents until notified by the Sponsor, and at least for 15 years after study completion, as per the Sponsor's requirements. Subject files and other source data (including copies of protocols, CRFs, original reports of test results, correspondence, records of informed consent, and other documents pertaining to the conduct of the study) must be kept for the maximum period of time permitted by the institution. Documents should be stored in such a way that they can be accessed/data retrieved at a later date, either in paper or electronically. Consideration should be given to security and environmental risks.

No study document will be destroyed without prior written agreement between the Sponsor and the investigator.

Protocol No: Version 2.17 Date: 17 October 2022

#### 11. ADMINISTRATIVE MATTERS

#### 11.1 Source Data

Source documents comprise the CRF and hospital records, laboratory records and correspondence. All documents will be stored safely in a confidential manner at the performing site. The subject will be referred to by a unique study subject number/code, their initials and date of birth on all study-specific documentations. The only exceptions will be the signed Consent Forms, Subject Identification log and subject clinical file, all of which will be stored securely by the clinical site. Source data will be made available for internal and external audits or inspections by regulatory authorities to authorised personnel only.

As a minimum requirement the following data must be source data verifiable in source documentation other than the eCRF:

- Existence of subject (subject identifier, subject number and date of birth)
- Confirmation of participation in the trial (subject identification number (ID), trial ID and signed and dated informed consent forms)
- Diagnosis/ indication under investigation
- Visit dates
- Data from AEs, safety information form and pregnancy forms
- Relevant medical history, concomitant illness
- Reason for exclusion or withdrawal

#### 11.2 Language

CRFs will be in German. Generic names for concomitant medications should be recorded in the CRF wherever possible. All written material to be used by subjects must use vocabulary that is clearly understood, and be in the language appropriate for the study site.

#### 11.3 Data Collection

All data collected will be documented in the source documents and eCRF (Clincase).

#### 11.4 Electronic Recording of data

This study will capture and process data using Clincase (electronic data capture) which will be built by Institute for Medical Informatics, Statistics and Documentation, Medical University of Graz. Clincase is a fully validated high quality electronic data capture system, which has a full audit trail and controlled level of access. Data and reports will be extracted from the database throughout the study to monitor progress and training will be provided to all study staff on use of the database. The Investigator must ensure that the data is recorded in the eCRFs as soon as possible after the visit preferably within 7 working days.

Protocol No: Version 2.17

#### Date: 17 October 2022

## 11.5 Study Management Structure

## 11.5.1 Trial Steering Committee (TSC)

A Trial Steering committee (TSC) comprised by all principal investigators and chaired be the Co-Chief investigators will be responsible for overseeing the progress of the trial. A TSC Charter will be devised to list the roles and responsibilities of the TSC members. TSC will be convened at least biannually either in person or by teleconference.

#### 11.6 Monitoring

A monitoring plan will be devised based on risk analysis and described in detail in the monitoring manual. During the course of the trial the Monitor will visit the trial sites to ensure that the protocol is adhered to, that all issues have been recorded and to perform source data verification. The study will be monitored periodically by a Clinical Trial Monitor responsible for this study.

Initiation visits will be completed at all trial centres prior to the recruitment of participants, and will consist of review of protocol and trial documents, training with respect to trial procedures (informed consent, SAE reporting, inclusion and exclusion criteria), review of recruitment strategy, review of site facilities and equipment, review of GCP principles, essential document receipt, collection and filing, and archiving and inspection. Copies of the trial specific procedure manuals and related documents will be given to the investigators. The approved version of the protocol should be followed at all times, and any significant protocol deviations will be documented in a Protocol Deviation Form and any significant deviations will be recorded on a Protocol Violation Form submitted to the study coordination centre and Sponsor as soon as possible. The investigators will allow the monitors to:

- inspect the site, the facilities, device management and materials used for the trial
- meet all members of the team involved in the trial, and ensure all staff working on the trial are experienced and appropriately trained, and have access to review all of the documents relevant to the trial
- have access to the electronic case record forms and source data
- discuss with the investigator and site staff trial progress and any issues on a regular basis

#### The monitor will ensure that:

- A percentage of records will be inspected for confirmation of existence, eligibility based on the results of the Risk Assessment
- 100 % of consent forms will be reviewed along with all SAE's.
- there is adherence to the protocol, including consistency with inclusion/exclusion criteria
- there is GCP and regulatory compliance
- trial documentation is complete and up to date (e.g. correct versions of documents being used, source data captured) and relevant documents are collected for the Trial Master File (TMF)
- the monitored eCRFs have been completed correctly and accurately, and all entries correspond to data captured in source documents

The Monitor must be given direct access to the source documents (original documents, data and records). Direct access includes permission to examine, analyse, verify and reproduce and record reports that are important to evaluation of the clinical trial.

Protocol No: Version 2.17 Date: 17 October 2022

All information dealt with during such visits will be treated as strictly confidential. At the end of the trial, close out visits will be performed by the monitor after the final participant visit has been completed and prior to database lock. During this visit the monitor will verify that all trial close out activities are completed – all queries resolved, missing data completed, monitoring completed, archiving arrangements in place, ISF completed and TMF documents collected, and end of trial notification. Each investigator will also be notified that an audit or inspection may be carried out - by the sponsor, sponsor's representatives or the host institution, or regulatory authorities - at any time, before, during or after the end of the trial. The investigator must allow the representatives of the audit or inspection team:

- to inspect the site, facilities and material used for the trial,
- to meet all members of his/her team involved in the trial,
- to have direct access to trial data and source documents, to consult all of the documents relevant to the trial. If an Investigator is informed of an impending audit or inspection, the trial coordination centre should be notified immediately.

## 11.7 Disclosure of data and publication

Information concerning the study, patent applications, processes, scientific data or other pertinent information is confidential and remains the property of the Sponsor. The investigator may use this information for the purposes of the study only. Verbal or written discussion of results prior to study completion and full reporting should only be undertaken with written consent from the Sponsor. Therefore all information obtained as a result of the study will be regarded as CONFIDENTIAL, at least until appropriate analysis and review by the investigators is completed. Permission from the Trial Steering Committee is necessary prior to disclosing any information relative to this study outside of the Steering Committee.

## Appendix A Power and sample size calculation

endocrinology

Power and sample size calculation for the project: Impact of Empagliflozin on cardiac function and biomarkers of heart failure in patients with acute myocardial infarction with or without type 2 diabetes

# 1 Introduction

endocrinology

The objective here is to show the steps followed to derive the sample size when using the change, from baseline to 6 months, in the levels of NT-proBNP as the primary endpoint.

Let  $X_0^{n_1} = (X_{01}, X_{02}, ..., X_{0n_1})$  and  $X_1^{n_1} = (X_{11}, X_{12}, ..., X_{1n_1})$  be the samples at baseline and at follow-up (6 months) in the placebo group and  $Y_0^{n_2} = (Y_{01}, Y_{02}, ..., Y_{0n_2})$  and  $Y_1^{n_2} = (Y_{11}, Y_{12}, ..., Y_{1n_2})$  be the samples at baseline and at follow-up (6 months) in the treatment group. We assume the following distributional assumptions:

$$X_{0i} \sim N(\theta_0, \sigma_{0x}^2) i = 1, 2, ..., n_1$$
 (1.1)

$$X_{1i} \sim N(\theta_1, \sigma_{1x}^2) i = 1, 2, ..., n_1$$
 (1.2)

$$Y_{0i} \sim N(\gamma_0, \sigma_{0y}^2) i = 1, 2, ..., n_2$$
 (1.3)

$$Y_{1i} \sim N(\gamma_1, \sigma_{1y}^2) i = 1, 2, ..., n_2$$
 (1.4)

Let us define  $X_t = X_{0t} - X_{1t}$   $i = 1, 2, ..., n_1$  and  $Y_t = Y_{0t} - Y_{1t}$   $i = 1, 2, ..., n_2$  as the change from baseline to follow-up in the placebo and treatment group respectively. Then from equations (1.1), (1.2), (1.3) and (1.4) we have that:

$$X_i \sim N(\theta = (\theta_0 - \theta_1), \sigma_x^2) i = 1, 2, ..., n_1$$

$$Y_i \sim N(\gamma = (\gamma_0 - \gamma_1), \sigma_v^2) i = 1, 2, ..., n_2$$

where  $\sigma_x^2 = \text{var}(X_t)$  and  $\sigma_y^2 = \text{var}(Y_t)$  are the variance of the change over time in the placebo and treatment group respectively. In this framework, we assume that these two variances are equal. More specifically, we assume that:

$$\sigma_x^2 = \sigma_y^2 = \sigma_c^2 \qquad (1.5)$$

This assumption of a common variance of the change over time can be easily satisfied by assuming that: 1- the correlation between baseline and follow-up measurements is the same in the placebo and treatment groups and 2- the ratio of the follow-up and baseline variances is the same in the placebo and treatment groups. To show this, let's first note that:

$$\sigma_x^2 = \text{var}(X_i) = \text{var}(X_{0t} - X_{1t})$$
  
 $= \text{var}(X_{0t}) + \text{var}(X_{1t}) - 2cov(X_{0t}, X_{1t})$   
 $= (1 + m_x - 2r_x\sqrt{m_x})\sigma_{0x}^2$  (1.6)

and similarly that  $\sigma_y^2 = \text{var}(Y_t) = (1 + m_y - 2r_y\sqrt{m_y})\sigma_{0y}^2$  where  $m_x$  (respectively  $m_y$ ) is the ratio of the baseline and follow-up variances in the placebo (respectively. treated) group and  $r_x$  (respectively  $r_y$ ) is the correlation coefficient between baseline and follow-up measurements in the placebo (respectively. treated) group. The assumption of equal variances for the change in (1.5) is satisfied if:

$$m_x = m_y = m, r_x = r_y = r \text{ and } \sigma_{0x}^2 = \sigma_{0y}^2 = \sigma_0^2$$
(1.7)

Protocol No: Version 2.17 Date: 17 October 2022

# 2 Sample size calculation

endocrinology

In this study we want to test the null hypothesis that the average change in the level of the biomarker (NT-proBNP) is the same in the treated compared to the placebo group. More specifically, let  $\Delta = \theta - \gamma = (\theta_0 - \theta_1) - (\gamma_0 - \gamma_1)$ . We want to carry out the following test:

$$H_0: \Delta = 0 \Leftrightarrow (\theta_0 - \theta_1) = (\gamma_0 - \gamma_1)$$
  
against  
 $H_1: \Delta \neq 0 \Leftrightarrow (\theta_0 - \theta_1) \neq (\gamma_0 - \gamma_1)$  (2.8)

# 2.1 Formula for the sample size calculation

The null hypothesis in (2.8) can be tested by using the standard t-test for comparing two averages. The formula for the required sample size can be analytically derived as follows:

$$n_1 = kn_2$$
 with  $n_2 = \frac{(z_{\frac{\alpha}{2}} + z_{\beta})^2 \sigma_c^2}{\Delta^2} (1 + \frac{1}{k})$  (2.9)

where k is the sample size ratio (assumed here equal to 1),  $\alpha$  and  $1 - \beta$  are the significance level and the power of the test and  $\sigma_c^2$  is the common variance for the change over time as defined in (1.5).

To derive the required sample size in (2.9), one need to specify a minimal clinically relevant value for  $\Delta$  and obtain an estimate of the common variance of the change  $\sigma_c^2$ . In what follows we show how one can derive estimates of these parameters.

# 2.2 Derivation of $\sigma_c^2$ and $\Delta$

Using equation (1.6) and assumption (1.7), one can easily derive the common variance as follows:

$$\sigma_c^2 = (1 + m_x - 2r_x\sqrt{m_\tau})\sigma_{0x}^2$$
(2.10)

where  $\sigma_{0x}^2$  is the variance at baseline in the placebo group,  $m_x = \frac{\sigma_{1x}^2}{\sigma_{0x}^2}$  is the variance ratio between follow-up and baseline in placebo group and  $r_x$  is the correlation coefficient between follow-up and baseline measurements in the placebo group. Also, one can express  $\Delta$  as a function of the desired relative reduction RR by  $\Delta = (\theta_0 - \theta_1)RR$  where  $RR = \frac{(\theta_0 - \theta_1) - (\gamma_0 - \gamma_1)}{\theta_0 - \theta_1}$ is the desired relative reduction associated to treatment.

Now, one can estimate the parameters needed for the sample size calculation *i.e.*  $\Delta$  and the common variance of the change  $\sigma_c^2$  by finding estimates of the means  $\theta_0$  and  $\theta_1$ , variances  $\sigma_{0x}^2$  and  $\sigma_{1x}^2$  and correlation  $r_x$  from previous studies. In practice unfortunately, not all studies report summary results in terms of means, standard deviations and correlations. This is for instance the case of our study where previous similar studies reported only quartiles and sample size at baseline and follow-up. The next question is then how can we approximate means and variances using quartiles and sample size. To do this, we used the approximation

Protocol No: Version 2.17

Date: 17 October 2022

results in [1]. According to [1], the mean  $\mu$  and standard deviation  $\sigma$  can in general be approximated from the quartiles and sample size as follows:

$$\hat{\mu} \approx \frac{q_1 + q_2 + q_3}{3}$$
(2.11)

$$\hat{\mu} \approx \frac{q_1 + q_2 + q_3}{3}$$

$$\hat{\sigma} \approx \frac{q_3 - q_1}{2\Phi^{-1}(\frac{0.75n - 0.125}{n + 0.25})}$$
(2.11)

where  $q_1$ ,  $q_2$  and  $q_3$  are respectively the first, second (median) and the third quartiles, n is the sample size and  $\Phi^{-1}(.)$  is the cdf inverse of a unit Gaussian distribution.

# Application to our project

According to a similar study [2] that reported the quartiles of NT-proBNP at baseline and at 6 months follow-up and using the approximations in (2.11) and (2.12), the estimates of the parameters needed for the sample size calculation are as follows:

$$\theta_0 \approx \frac{201 + 518 + 1242}{3} = 653.66$$

$$\theta_1 \approx \frac{113 + 232 + 503}{3} = 282.66$$

$$\sigma_{0x} = \frac{1242 - 201}{2\Phi^{-1}(\frac{0.75.877 - 0.125}{877 + 0.25})} = 772.98$$

$$\sigma_{1x} \ = \ \frac{503 - 113}{2\Phi^{-1}(\frac{0.75.856 - 0.125}{856 + 0.25})} = 289.60$$

$$m_x = \frac{\sigma_{1x}^2}{\sigma_{0x}^2} = 0.14$$

Assuming  $\alpha = 5\%$  and a power  $1 - \beta = 80\%$ , the required sample size as a function of the correlation between baseline and follow-up measurements is given in tables 1, 2 and 3 according to different levels of the desired relative reduction RR = 0.3, 0.35 and 0.4.

Protocol No: Version 2.17 Date: 17 October 2022

Table 1: Sample size as a function of the correlation between baseline and follow-up measurements using a relative reduction RR=0.3

res	Correlation coefficient	Sample size in each arm	Total sample size
1	0.00	865	1730
2	0.05	837	1674
3	0.10	808	1616
	0.15	780	1560
5	0.20	751	1502
6	0.25	723	1446
4 5 6 7 8	0.30	695	1390
8	0.35	666	1332
9	0.40	638	1276
10	0.45	610	1220
11	0.50	581	1162
12	0.55	553	1106
13	0.60	524	1048
14	0.65	496	992
15	0.70	468	936
16	0.75	439	878
17	0.80	411	822
18	0.85	383	766
19	0.90	354	708
20	0.95	326	652
21	1.00	298	596

Table 2: Sample size as a function of the correlation between baseline and follow-up measurements using a relative reduction RR=0.35

res	Correlation coefficient	Sample size in each arm	Total sample size
1	0.00	636	1272
2	0.05	615	1230
	0.10	594	1188
4	0.15	573	1146
5	0.20	552	1104
6	0.25	532	1064
7	0.30	511	1022
8	0.35	490	980
9	0.40	469	938
10	0.45	448	896
11	0.50	427	854
12	0.55	407	814
13	0.60	386	772
14	0.65	365	730
15	0.70	344	688
16	0.75	323	646
17	0.80	302	604
18	0.85	282	564
19	0.90	261	522
20	0.95	240	480
21	1.00	219	438

Protocol No: Version 2.17 Date: 17 October 2022

Table 3: Sample size as a function of the correlation between baseline and follow-up measurements using a relative reduction RR = 0.4

res	Correlation coefficient	Sample size in each arm	Total sample size
1	0.00	487	974
2	0.05	471	942
3	0.10	455	910
4	0.15	439	878
5	0.20	423	846
6	0.25	407	814
7	0.30	391	782
8	0.35	375	750
9	0.40	359	718
10	0.45	344	688
11	0.50	328	656
12	0.55	312	624
13	0.60	296	592
14	0.65	280	560
15	0.70	264	528
16	0.75	248	496
17	0.80	232	464
18	0.85	216	432
19	0.90	200	400
20	0.95	184	368
21	1.00	168	336

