#### 7. STATISTICAL ANALYSES

#### 7.1 Sample size and power considerations

Previous data showed that nt-proBNP levels decrease by about 50% within 6 months after acute myocardial infarction. To detect a relative 40% larger reduction in nt-proBNP levels in the Empagliflozin group as compared to the placebo group with a power of 80% and an alpha-level of 0.05%, and assuming a correlation for nt-proBNP levels of 0.85, a sample size of 216 subjects in each group is necessary. To account for a dropout rate of about 10% each group will consist of 238 patients.

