#### 7.2 Data analysis

Patient characteristics will be summarized. Summaries of continuous variables will be presented as means and standard deviations, if normally distributed, and as medians and inter-quartile ranges for skewed data, whilst categorical variables will be presented as frequencies and percentages. The analysis will be performed according to the intention to treat principle. All statistical tests will be two-tailed with a 5% significance level.

Analysis will be based on the intention to treat cohort, while a sensitivity analysis for the per-protocol group will be done in addition. A detailed statistical analysis plan including pre-specified subgroup analyses will be finalized ahead of database lock.

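### Appendix A derives its SDs from right-skewed NT-proBNP quartiles with formulas for normal data, so 80% power is not established for the raw-change t-test and does not describe the baseline-adjusted primary analysis

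*Protocol*

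**What the plan says.** Protocol section 7.1 justifies the trial's size by its ability "To detect a relative 40% larger reduction in nt-proBNP levels in the Empagliflozin group as compared to the placebo group", with 80% power and "assuming a correlation for nt-proBNP levels of 0.85". This gives 216 per arm, raised to 238 for dropout. SAP section 4 repeats the statement.

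The derivation is in Protocol Appendix A:

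- Section 1 introduces its model with "We assume the following distributional assumptions" and then takes NT-proBNP as normal at baseline and follow-up in both arms.
- Section 2.1 sizes a two-sample t-test on raw change from baseline.
- Section 2.2 explains that "previous similar studies reported only quartiles and sample size at baseline and follow-up". It approximates each mean by the average of the three quartiles, and each SD by the interquartile range divided by twice a Gaussian quantile. It defines the target difference Δ as the relative reduction RR times the mean fall under placebo.
- Section 3 applies this: "using the approximations in (2.11) and (2.12), the estimates of the parameters needed for the sample size calculation are as follows". The inputs are 201/518/1242 (n = 877) and 113/232/503 (n = 856).

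The appendix does not discuss skewness. The planned analysis differs from the test that was sized. SAP section 7.1 specifies a mixed model with baseline NT-proBNP as a fixed effect, and SAP section 5.3.1 says only that a log transformation might be used if the data are not normal.

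**The concern.** An interquartile range converted with a Gaussian quantile gives the right SD only if the data are close to normal. For a positive, right-skewed marker most of the variance of a raw change sits in the upper tail, which the interquartile range does not see. The quartiles themselves show the problem, and so does a derived baseline SD (773) that exceeds the mean (654) for a quantity that cannot be negative.

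The required n is proportional to the variance of change, so any understatement of the SD passes directly into the 216 and the 80%. Those two figures are the only stated justification of the trial's size, and a reader uses them to judge what the trial can detect.

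**Working it through.** **1. Reproduce the plan's figure.** Inputs are from Appendix A section 3: means 653.67 and 282.67, SDs 772.98 and 289.60, RR = 0.40, r = 0.85, two-sided alpha 5%.

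- Δ = 0.40 × (653.67 − 282.67) = 148.4
- SD of change = √(772.98² + 289.60² − 2 × 0.85 × 772.98 × 289.60) = 548.5
- n = 2 × 7.849 × 548.5² / 148.4² ≈ 215 per arm, against 216 stated. Power at 216 is 80.3%.

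The arithmetic is sound. (Protocol 7.1 and SAP 4 print alpha as 0.05%. Appendix A uses 5%, Protocol 7.2 says "All statistical tests will be two-tailed with a 5% significance level", and only 5% gives 216; 0.05% would need 511 per arm. That is a separate correction.)

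**2. Test normality against the quartiles.**

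- Upper over lower half of the interquartile range: (1242 − 518)/(518 − 201) = 2.28 and (503 − 232)/(232 − 113) = 2.28. A normal gives 1.
- The derived normals put Φ(−653.67/772.98) = 20% and Φ(−282.67/289.60) = 16% of patients below zero.
- The derived baseline normal has quartiles 132/654/1175, not 201/518/1242.
- On the log scale the same half-range ratios are 0.92 and 1.08, close to symmetric.

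**3. Refit with a log-normal.** Log-SD = ln(q3/q1)/(2 × 0.6745), which gives 1.350 and 1.107. Mean = median × exp(s²/2) and SD = mean × √(exp(s²) − 1).

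- Baseline: mean 1,289, SD 2,935 (3.8 times 773)
- 6 months: mean 428, SD 664 (2.3 times 290)
- SD of change with raw r = 0.85: √(2935² + 664² − 2 × 0.85 × 2935 × 664) = 2,396 (4.4 times). If 0.85 is instead the log-scale correlation, the raw r is 0.725 and the SD is 2,496 (4.6 times).
- Δ by the rule of Appendix A section 2.2: 0.40 × (1,289 − 428) = 344
- Power at 216 is 32% or 30%, and 80% power needs 761 or 826 per arm. With Δ held at 148.4, power is about 9% to 10%.

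**4. Vary the tail.** Results with r = 0.85 (log-scale r for the capped rows):

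| Distribution | SD of change, times the plan's | Power, Δ rescaled | Power, Δ = 148.4 |
|---|---|---|---|
| Gamma | 1.28 | 87% | 59% |
| Weibull | 1.41 | 83% | 51% |
| Log-normal capped at 95th percentile | 1.8 | 80% | 35% |
| capped at 97.5th | 2.3 | 68% | 24% |
| capped at 99th | 2.8 | 56% | 17% |
| capped at 99.5th | 3.2 | 50% | 14% |
| uncapped | 4.4 to 4.6 | 30-32% | 9-10% |

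The gamma (197/548/1200; 110/250/481) and Weibull (197/543/1209; 109/251/482) fits come within about 8% of every quartile. A chi-square test based on the sampling covariance of quartiles at the stated n (1 df, parameters refitted) separates them better. The log-normal is compatible at both visits (p = 0.39 and 0.43). Weibull gives p = 0.09 and 0.001, gamma 0.04 and 0.001. The normal is rejected (chi-square 67 and 65).

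**5. Detectable effect with baseline adjustment on the log scale.** The detectable log difference is 2.802 × 1.107 × √(1 − r²) × √(2/216), with 216 per arm and 80% power:

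| r (log scale) | Week-26 geometric mean lower by |
|---|---|
| 0.85 | 14.5% |
| 0.7 | 19% |
| 0.5 | 23% |
| 0.3 | 25% |

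For comparison, the plan's own target is a week-26 mean of 282.67 − 148.4 = 134.3, which is 52.5% lower than placebo.

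**The case against.** The strongest reply is that the documents hold three quartiles per visit and nothing about the tail, so the large figures are extrapolation. In the uncapped log-normal the top 1% of baseline values supply about 71% of the variance, and no document describes that 1%. Gamma and Weibull fits, also right-skewed, leave power at or above 80% once Δ is rescaled. This stands. A reader might infer from step 3 that the SD is understated fourfold and that true power is one third. The documents do not support that as a fact: it needs an uncapped log-normal together with a rescaled Δ, and even then the 6-month SD rises only 2.3 times. The better quartile fit of the log-normal favours the upper end of the range but cannot settle the tail.

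The second reply is that the t-test on raw change is not the planned analysis. This stands too, and it defeats a second tempting inference, that the trial is underpowered or needs more patients. In simulations of the same log-normal at the rescaled effect, the raw-change t-test had 34% to 47% power, while a two-visit baseline-adjusted comparison had close to 100%. That effect is very large (344 of 428, an 80% lower mean), so step 5 is the better guide to what 216 per arm can detect.

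Neither reply rescues the stated 80%. Every skewed fit gives a larger SD of change than 548, and the figure was not calculated for the baseline-adjusted model. Nor is recalculating Δ an arbitrary choice: Appendix A section 2.2 ties it to the mean fall, so new means give a new Δ, and keeping 148.4 lowers the power under every fit in the table.

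**Conclusion.** The concern holds in a limited form. The planning inputs rest on a normality assumption that the plan's own source quartiles contradict. The SD of change is probably understated, by a factor that could lie anywhere from about 1.3 to 4.6. Power of the raw-change t-test at 216 per arm is therefore not established as 80%. It lies between about 30% and 87% with Δ recalculated as 40% of the fitted mean fall, and between about 10% and 59% with Δ held at 148.4.

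These ranges assume that the source quartiles apply to this trial's population and that the correlation is 0.85. The distributions above the upper quartile are assumptions, not data. The finding concerns the inputs and the stated power, not the adequacy of N.

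**What to change.** Keep N. In Appendix A section 3, Protocol section 7.1 and SAP section 4:

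- Replace the normal-theory means and SDs with log-scale values from the same quartiles (medians 518 and 232, log-SDs 1.350 and 1.107), and state that they assume a log-normal distribution.
- Restate power for a baseline-adjusted comparison on the log scale: 216 per arm gives 80% power for a week-26 geometric mean about 14.5%, 19%, 23% or 25% lower at r = 0.85, 0.7, 0.5 or 0.3. Show the whole range, because a correlation of 0.85 is assumed, not estimated. Say also that these figures apply to a log-scale analysis, which SAP section 5.3.1 leaves conditional.
- Remove the unqualified claim of 80% power for a 40% larger raw reduction.

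The cost is one appendix section and a sentence in each of two places, with no extra patients or visits.
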